5.5. COST OF THE REGISTRY

Efforts to enhance efficiency are driven, in part, by potential cost savings. In SEARCH 4, we will conduct a prospective assessment in the two parallel aspects of SEARCH: conventional case ascertainment (Aims 1-3) and the D&V projects (Aim 4) in order to estimate the cost of case registration. The primary means of data collection will be the time diary in which staff members will be asked to record all SEARCH activities over a typical work week, periodically over time, with attention to infrequent tasks (e.g., those conducted monthly). The types of activities to be tracked include: managing people, clerical (mailing, logging, filing), training of staff, IT support, meetings, locating/reviewing/entering data, identification/validation/deduplication/registration, analyzing/generating reports, and local travel. For the conventional case ascertainment, diaries will be completed one week each quarter, over a period of one year. For the D&V projects, diaries will be completed more frequently, depending upon the length of the project. Actual salary and benefit rates will be applied to the time elements. A count of the number and type of cases registered during the

time period will be obtained from the SEARCH registration database. Specifically, we will evaluate time and cost for the Registry as it is currently conducted, then will systematically model the incremental differences that can be attributed to approaches determined to be valid from the D&V Projects.

6. Statistical Considerations

6.1. REGISTRY STUDY - STATISTICAL CONSIDERATIONS

6.1.1. Aim 1: Detectable Differences in Prevalence

The third assessment of the prevalence of diabetes in youth is scheduled for 2017. Similar to previous work, prevalence will be expressed as the number cases with T1 or T2D per 1,000 youth pooled across all SEARCH sites. Prevalence estimates will be derived by sex, age and by race/ethnicity groups within each diabetes type. Trends in prevalence will be assessed by comparing the 2017 estimates to those observed in 2009 and 2001. Poisson regression models will be fitted to incorporate results from all 3 surveys. Standard errors associated with the estimated change in prevalence rates between any 2 time points will be computed using a 2 sided skew-corrected inverted score tests for binomial distribution. Standard error for the trends in prevalence estimates will be derived from the Poisson regression model. This model will also be used to generate adjusted prevalence where adjustment will be made for race/ethnicity, age and sex. Our power calculation suggests that we are well-powered to detect changes in prevalence by diabetes type, and across race/ethnic group within each diabetes type. For example, we will have at least 90% power to detect a rate of change of 4.1% in NHW youth with T1D, and a rate of change of 19.1% in NHB youths with T2D for the period between 2009 and 2017.

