5.4. PROJECT #4: EXPANSION OF SURVEILLANCE TO ADDITIONAL AMERICAN INDIAN (AI) TRIBES

Since its inception in 2000, SEARCH has been conducting surveillance of youth onset diabetes in AI tribes under the direction of the Colorado site. These results indicate that AI youth have the highest incidence and prevalence of T2D of any major race/ethnic group (61, 6, 9). Unfortunately, the AI population under surveillance is the smallest of the major race/ethnic groups (~95,000 youth), and results in less than ~40 incident cases per year across all sites. The goal of this project is to develop and validate an algorithm that may be used to identify AI and possibly Alaskan Native (AN) youth with diabetes using data extracts from *existing* electronic health records (EHR) of the Indian Health Service (IHS). For the proposed pilot project, the SEARCH Colorado site will partner with the Center for AI AN Health (CAIANH), both located within the Colorado School of Public Health.

An algorithm will be developed to identify AI youth aged < 20 years with diabetes using IHS data that includes diagnostic codes, provider and service type information and dispensed medications. The algorithm will be developed from the IHS data for the Chinle and Tuba City Service Units on the Navajo Reservation and validated by comparison to the Navajo SEARCH registry (gold standard) for the same service units and will result in metrics for sensitivity, specificity, positive and negative predictive value. Next, and coordinated through CAIANH, the best algorithm developed in Phase 1 will be used to identify AI youth with diabetes in another IHS Service Unit, from a different tribe, using the same IHS National Data Warehouse.

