6.1.2. Aim 2: Detectable Differences in Incidence

A similar approach will be taken to estimate the incidence rates of diabetes by type, race/ethnicity, sex and age. Incidence rates will be estimated as the number of diagnosed cases across all sites divided by the total number of individuals who are at risk across these sites. The incidence rates will be expressed in terms of the number of cases diagnosed per year per 100,000 individuals. Adjusted incidence rates will also be provided by race/ethnicity, sex and age. SEARCH 4 will add 5 additional years of incidence data taking the current time series from 12 to 17 years of data, thereby providing improved power to detect changes in incidence rate during this period for various subgroups. Based on our power calculations (see Table 5), SEARCH 4 will have 90% power to detect changes as small as 1.04% in NHW females with T1D and 2.1% in NHB females with T2D. However, we will have limited power to detect changes in API and AI youth. This is the rationale for D&V Project # 4 in which we propose an approach to develop a model for extension of the SEARCH Registry to increase inclusion of population subgroups for which our sample size is limited.

Table 5.: Detectable rate of change in incidence rate by diabetes type, sex and race/ethnicity, and power							
Race Sex Type 1 Type 2							
Nace	JEA	90%	80%	90%	80%		
	All	0.6	0.5	1.1	0.9		
All	F	0.9	0.8	1.4	1.2		
	М	0.8	0.7	1.8	1.5		
	All	0.7	0.6	2.5	2.2		
NHW	F	1.0	0.9	3.2	2.8		
	М	1.0	0.9	4.0	3.4		
	All	1.5	1.3	2.0	1.7		
Hispanic	F	2.1	1.8	2.6	2.2		
	М	2.1	1.8	3.1	2.7		
	All	1.9	1.6	1.8	1.5		
NHB	F	2.7	2.3	2.1	1.8		
	М	2.7	2.3	3.4	2.9		
	All	4.7	4.1	4.7	4.1		
API	F	7.4	6.4	6.9	6.0		
	М	6.1	5.3	6.5	5.6		
	All	8.0	6.9	4.2	3.6		
AI	F	11.4	9.8	6.6	5.7		
	М	11.2	9.6	5.3	4.6		

Detecting a "leveling off" of T1D incidence in NHW Youth. The first 8 years of incidence data collected during the 2002-2009 period suggests a linear trend with a constant rate of increase of about 3% per year. With the accumulation of 5 more years of data SEARCH could be in a position to detect potential changes in incidence trends, and estimate retrospectively the incident year when the change happened. Simulation studies were performed to assess the power to correctly identify the year corresponding to the change point. The simulation study started with the data that is already available in SEARCH, which was used to

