6.1.3. Aim 3: Detectable Differences in Prevalence of DKA

Assuming a significance level of 0.05, we have 80% power to detect an absolute change of 0.22% (from 30.3% to 30.1% for example) in the prevalence of DKA among T1D cases, and an absolute change of 0.25 (from 7.2% to 6.95%) in T2D cases. This analysis will be conducted after the completion of ascertainment efforts for the 2017 incident cohort.

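### Section 6.1.1 calls the registry well powered for prevalence change in race/ethnic groups within each diabetes type, with no exception for API and AI youth, whom Section 6.1.2 says it has limited power to study

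*Protocol*

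**What the plan says.** Section 6.1.1 plans to compare 2017 prevalence with 2009 and 2001 and to fit Poisson models to all three surveys. On power it says that "we are well-powered to detect changes in prevalence by diabetes type, and across race/ethnic group within each diabetes type". Two examples follow. The first is "at least 90% power to detect a rate of change of 4.1% in NHW youth with T1D". The second is a 19.1% change for NHB youth with T2D, with 2009 to 2017 named as the interval. No figure is given for API or AI youth, and neither group is excepted.

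Section 6.1.2, on incidence, says "we will have limited power to detect changes in API and AI youth" and gives this as the rationale for Development and Validation Project #4. Its Table 5 lists detectable incidence changes by type, sex and race/ethnicity. Section 5.4 puts the AI population under surveillance at about 95,000 youth and says that this "results in less than ~40 incident cases per year across all sites", without separating diabetes types.

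**The concern.** The two sections describe the same registry and the same subgroups. Section 6.1.2 discloses that API and AI numbers are small. Section 6.1.1 makes a subgroup power claim that leaves no room for that, and both of its examples come from much larger groups.

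The claim bears on a named question. Registry Research Question 1.2 asks how prevalence trends differ by race/ethnicity, and Section 5.4 says AI youth have the highest T2D prevalence of any major group. If the general claim stands, a non-significant API or AI change could be given more weight than the data allow.

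**Working it through.** **Inputs**

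- Stated detectable prevalence changes at 90% power (Section 6.1.1): 4.1% for NHW T1D and 19.1% for NHB T2D. I read both as 2009–2017 changes.
- Test: Section 6.1.1 names "2 sided skew-corrected inverted score tests for binomial distribution". It states no alpha. I assume 0.05, the level given in Section 6.1.3.
- Table 5, both sexes, 90% power, T1D/T2D: NHW 0.7/2.5; NHB 1.9/1.8; API 4.7/4.7; AI 8.0/4.2; all groups 0.6/1.1.
- Table 2: 1,652 incident cases in 2016.
- Not given: prevalent cases by race/ethnicity and type. Table 2 has only 1,004 additional 2017 prevalent cases, all groups together.

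**Step 1. The protocol's own figures.** They cannot be reproduced forward without prevalent counts. Back-solving a two-survey Poisson comparison with equal counts c, ln(RR) = (1.960 + 1.282) × √(2/c):

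- 4.1%: c = 2 × (3.2415 / ln 1.041)² ≈ 13,016 NHW T1D cases per survey.
- 19.1%: c = 2 × (3.2415 / ln 1.191)² ≈ 688 NHB T2D cases per survey.

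Nothing here shows that either figure is miscalculated.

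**Step 2. Scale the stated figures by Table 5.** This needs no case counts. It assumes that, within a diabetes type, groups stand in the same ratio for prevalence as for incidence. Scaled log change L = ln(1 + stated change) × (Table 5 value for the group ÷ value for the example group). Detectable change = exp(L) − 1. Power for 19.1% = Φ(0.1748 × 3.2415 / L − 1.960), where 0.1748 = ln 1.191.

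| Group | Table 5 ratio | L | Detectable change, 90% power | Power for 19.1% |
|---|---|---|---|---|
| API T1D | 4.7/0.7 = 6.71 | 0.0402 × 6.71 = 0.270 | 31% | 0.56 |
| AI T1D | 8.0/0.7 = 11.43 | 0.0402 × 11.43 = 0.459 | 58% | 0.23 |
| API T2D | 4.7/1.8 = 2.61 | 0.1748 × 2.61 = 0.456 | 58% | 0.24 |
| AI T2D | 4.2/1.8 = 2.33 | 0.1748 × 2.33 = 0.408 | 50% | 0.28 |

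Taking the ratios on the log scale instead gives 30%, 56%, 57% and 50%. Table 5 is rounded to one decimal. Moving each entry by 0.05 in the unfavourable or favourable direction gives 28–34%, 53–65%, 55–61% and 48–53%.

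**Step 3. Check through case counts.** Inverting Table 5 as a 17-year Poisson trend, annual cases = (3.2415 / ln(1 + d))² / 408, where d is the Table 5 value as a proportion. The all-groups rows give 719.7 + 215.2 = 934.9 cases a year, below Table 2, so the counts are multiplied by 1,652 / 934.9 = 1.767. This yields about 21.6 API cases a year of each type, 7.7 AI T1D and 26.9 AI T2D. The AI total of 34.6 is consistent with Section 5.4.

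Prevalent cases are then annual cases times an assumed number of years that a case remains in the prevalent pool:

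| Assumed years (T1D; T2D) | API T1D | AI T1D | API T2D | AI T2D |
|---|---|---|---|---|
| 13; 6 | 32% | 58% | 50% | 44% |
| 6 to 8; 2.5 to 5 | 42–50% | 79–96% | 55–87% | 48–75% |

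With 13 and 6 years the same method gives 4.2% for NHW T1D and 17% for NHB T2D, close to the stated 4.1% and 19.1%. With 6 to 8 years it gives 5–6% for NHW T1D, so the second row is probably pessimistic for T1D.

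**Step 4. Three surveys.** With equal counts in 2001, 2009 and 2017 and a constant log-linear trend, the variance of the slope per 8 years is 1/(2c), against 2/c for the two-survey contrast. The standard error is halved, and so is L. Detectable change per 8 years becomes about 14% (API T1D), 26% (AI T1D), 26% (API T2D) and 23% (AI T2D). Power for a trend of 19.1% per 8 years would be about 0.99, 0.69, 0.70 and 0.79. That trend amounts to 1.191² − 1 = 42% over 16 years. On the same footing NHB T2D would detect about 9%, so the gap between groups remains.

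**The case against.** The strongest objection concerns the numbers. The protocol gives no prevalent counts by race/ethnicity and type, and its only group-specific case count is AI incidence with both types combined. A reader might infer that the protocol's own case counts fix the detectable change for API and AI youth at some definite range, such as 40–80%. They do not. Every figure above needs a transfer from incidence to prevalence or an assumed duration, and API T1D falls to about 30% on the scaling route. This limits the precision of the point, but every two-survey route above leaves all four cells well above 19.1%.

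Second, the admission in Section 6.1.2 is about incidence, so it does not directly contradict a statement about prevalence. That is correct. But the limitation it describes is small group size, and nothing in the protocol suggests that prevalence escapes it.

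Third, Research Question 1.2 concerns trends over three surveys, which step 4 shows to be appreciably more precise. This stands. It does not rescue the sentence, because its worked figures are for 2009–2017 and three of the four cells stay below 80% power for 19.1% per 8 years, even with equal counts and a constant trend.

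Finally, a reader might infer that null API or AI results will be reported as stability. The protocol does not say so, and the open caveat in the next section makes it less likely. The risk follows from the wording; it is not a planned misreport.

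**Conclusion.** The power claim in Section 6.1.1 is too broad. It is not supported for API and AI youth, and it sits badly with Section 6.1.2, Table 5 and Section 5.4. The contradiction rests on the text and Table 5 alone: detectable incidence changes in these groups are about 2.3 to 11 times those of the groups used as examples.

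The size is approximate. For the 2009–2017 comparison at 90% power and two-sided 0.05, it is about 30% for API T1D and 50–58% for the other three cells, with power of roughly 0.23 to 0.56 for a 19.1% change. This assumes that the Table 5 ratios carry over to prevalence. Across the duration assumptions tried, the range is about 30% to nearly 100%. A sustained three-survey trend would be detected at roughly half the two-survey log change per 8 years.

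The finding is an over-broad statement that should be corrected. It shows no arithmetic error in 4.1% or 19.1%, and no flaw in the design or data collection.

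**What to change.** In Section 6.1.1:

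1. Limit the statement about adequate power to the groups for which it was calculated, and name them.
2. Add a small table of detectable prevalence changes by diabetes type and race/ethnicity, parallel to Table 5. Base it on the registry's actual prevalent counts, show the 2009–2017 comparison and the three-survey trend separately, and state alpha.
3. Carry over the Section 6.1.2 caveat for API and AI youth.
4. State that prevalence changes in these groups will be reported as estimates with confidence intervals, and that a non-significant change is inconclusive.

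The cost is a few sentences and one table from counts that the registry should already hold for the earlier surveys. Sampling, data collection and the planned models do not change. The stated power becomes less favourable for two groups.

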6.1.2. Aim 2: Detectable Differences in Incidence

A similar approach will be taken to estimate the incidence rates of diabetes by type, race/ethnicity, sex and age. Incidence rates will be estimated as the number of diagnosed cases across all sites divided by the total number of individuals who are at risk across these sites. The incidence rates will be expressed in terms of the number of cases diagnosed per year per 100,000 individuals. Adjusted incidence rates will also be provided by race/ethnicity, sex and age. SEARCH 4 will add 5 additional years of incidence data taking the current time series from 12 to 17 years of data, thereby providing improved power to detect changes in incidence rate during this period for various subgroups. Based on our power calculations (see Table 5), SEARCH 4 will have 90% power to detect changes as small as 1.04% in NHW females with T1D and 2.1% in NHB females with T2D. However, we will have limited power to detect changes in API and AI youth. This is the rationale for D&V Project # 4 in which we propose an approach to develop a model for extension of the SEARCH Registry to increase inclusion of population subgroups for which our sample size is limited.

Table 5.: Detectable rate of change in incidence rate by diabetes type, sex and race/ethnicity, and power							
Race Sex Type 1 Type 2							
Nace	JEA	90%	80%	90%	80%		
	All	0.6	0.5	1.1	0.9		
All	F	0.9	0.8	1.4	1.2		
	М	0.8	0.7	1.8	1.5		
	All	0.7	0.6	2.5	2.2		
NHW	F	1.0	0.9	3.2	2.8		
	М	1.0	0.9	4.0	3.4		
	All	1.5	1.3	2.0	1.7		
Hispanic	F	2.1	1.8	2.6	2.2		
	М	2.1	1.8	3.1	2.7		
	All	1.9	1.6	1.8	1.5		
NHB	F	2.7	2.3	2.1	1.8		
	М	2.7	2.3	3.4	2.9		
	All	4.7	4.1	4.7	4.1		
API	F	7.4	6.4	6.9	6.0		
	М	6.1	5.3	6.5	5.6		
	All	8.0	6.9	4.2	3.6		
AI	F	11.4	9.8	6.6	5.7		
	М	11.2	9.6	5.3	4.6		

Detecting a "leveling off" of T1D incidence in NHW Youth. The first 8 years of incidence data collected during the 2002-2009 period suggests a linear trend with a constant rate of increase of about 3% per year. With the accumulation of 5 more years of data SEARCH could be in a position to detect potential changes in incidence trends, and estimate retrospectively the incident year when the change happened. Simulation studies were performed to assess the power to correctly identify the year corresponding to the change point. The simulation study started with the data that is already available in SEARCH, which was used to

fit Poisson regression models, which was then used to predict yearly incidence rates until 2018 assuming a linear trend. The model is then perturbed to mimic the effect of a change point that could occur respectively in 2012, 2013, 2014, 2015 and 2016. The perturbed model assumes that the reduction in incidence rate happened at the selected year and remained constant at the new rate in future years. This simulation process indicated that we will have ~70% power to detect a reduction of 5% in the incidence rate after 2016. It should be noted that the Finnish T1D registry study needed more than 30 years of data to be able to retrospectively identify 1988 and 2002 as the years where changes in the incidence rate happened, with only the change point observed in 1988 being statistically significant (62). Our proposed analysis will be conducted in the second half of 2019 – after the close of the 30 months window for the incident 2016 cases.

Adjusting Results for Potential Differences in Agreement between Provider Type and Etiologic Type Over Time. Estimation of incidence trends can be affected by potential temporal changes in provider assessment of diabetes type. Such changes can lead to biased estimation of the trend. We will test for homogeneity of association between diabetes type as assessed by the provider and SEARCH etiologic type over the time period, and adjust for the difference in agreement over time as needed.

6.1.3. Aim 3: Detectable Differences in Prevalence of DKA

Assuming a significance level of 0.05, we have 80% power to detect an absolute change of 0.22% (from 30.3% to 30.1% for example) in the prevalence of DKA among T1D cases, and an absolute change of 0.25 (from 7.2% to 6.95%) in T2D cases. This analysis will be conducted after the completion of ascertainment efforts for the 2017 incident cohort.

6.1.4. Aim 4: Adjusting Results Using Capture-Recapture Analysis

The completeness of ascertainment for each site will be estimated by dividing the number of identified cases by the estimated total number obtained from the capture-recapture analysis. The capture-recapture corrected estimate will be computed by dividing the observed incidence rate by the estimated capture-recapture rate. This corrected estimate can be seen as a ratio of 2 random variables. Pooled estimates that borrow information across site, sex and age groups will be used to guarantee that the capture-recapture rate and its associated standard error can be computed for all combinations of the variables considered in the analysis. Stratification by site, diabetes type, race/ethnicity, sex and age group can sometimes lead to small cell count causing convergence failures in the maximum likelihood estimation routines. Pooled estimation performed assuming a log-linear model makes it possible to obtain the maximum likelihood estimates in these cases and simplifies the derivation of the standard error associated with the estimated percentage completeness.

6.2. COHORT STUDY - STATISTICAL CONSIDERATIONS

6.2.1. Aim 1: Burden of Complications

Three main analytic approaches will be employed to examine the prevalence, incidence, progression and clustering of complications by diabetes type and responsible risk factors and pathways: a) estimating incidence and prevalence using multiple logistic regression methods; b) estimating the progression of complications using longitudinal mixed models; and c) estimating the clustering of risk factors and outcomes using longitudinal mixed models. For each of these approaches we will incorporate participant level characteristics, measured at multiple time points, to examine potential mediators and moderators of outcomes.

Incidence Rate Estimation: Participants have had at least two previous in-person visits (C_0, C_1) ; however, for many outcomes (retinopathy, neuropathy, etc.) participants will have had only one previous assessment (C1 visit). For these outcomes we will be able to define a group of participants who were free from the event of interest (e.g. no retinopathy) at C1. Multiple logistic regression methods will be employed to examine the incidence rates of binary measures, with categorical (e.g.T1D vs. T2D) or continuous (e.g. A1c) predictors. We will evaluate potential confounding and/or effect modification based on our extensive databases.

Prevalence Rate Estimation: Some of the outcomes of interest have not been measured previously (e.g. echocardiography); therefore, we will estimate the prevalence of these outcomes. Associations of risk factors and diabetes type with prevalent outcomes will be examined using logistic regression models.

Statistical Power: For each of the primary dichotomous outcomes of interest (incidence or prevalence) we estimated proportions that will have the specific outcomes of interest, based on data from the C₁ visit. Table 6 shows the expected sample sizes available for comparing T1D and T2D, the corresponding detectable differences in rates, and the power for each outcome. We also provide the expected detectable differences in prevalence rates of LV hypertrophy between T1D and T2D in the sample of patients receiving echocardiography. These calculations are performed using Fisher's exact tests with $\alpha = 0.05$ (2-sided).

Table 6. Power for detectable differences for primary outcomes								
Outcome	T1D/T2D available	T1D rate	T2D rate	Power				
	Incidence Comparisons							
Retinopathy	1215/230	10%	18%	88%				
Neuropathy	1344/283	5%	10%	81%				
Nephropathy	1172/268	20%	29%	85%				
Prevalence Comparisons (Cardiac echocardiography)								
LV hypertrophy	250/250	5%	13%	86%				

Longitudinal Models: We will use a longitudinal mixed effects analysis of covariance approach to make comparisons among groups which includes duration of diabetes as a time-varying covariate and participant as a random effect. This approach models the varying durations of disease prior to the initial visit, and the varying durations of time allowed by the data collection windows between visits. These mixed effects models are flexible to allow for non-linear relationships to be modeled over time, and permit random rates of progression.

To estimate the sample size needed to detect a significant difference with sufficient power, calculations were based on comparing measurements after adjusting for C_0 or C_1 data. If the correlation between measurements is moderate (0.50) then we have 80% power to detect a difference of 0.139 standard deviations (SD) for each outcome of interest. For example, based on data collected on a subset of SEARCH T1D participants, the standard deviation for PWV carotid-femoral was estimated to be 0.7 m/s, thus we would have 80% power to detect a difference of 0.10 m/s in progression of PWV between youth with T2D vs T1D.

Clustering of Outcomes: In addition to examining each endpoint separately, we have the opportunity to look simultaneously at several outcomes in the same analysis. We

will create variables that describe the co-occurrence (clustering) of outcomes for each participant and examine whether there are differences in the patterns of these clusters between T1D and T2D youth. Approaches will utilize ordinal logistic regression methods or longitudinal mixed models depending on whether the clustering outcome is a count or categorical. More sophisticated statistical methods may also be used such as principal components analyses to determine which risk factors may form different components.

